Subjects without events will be censored at the earliest of the study cut-off date, last contact date, or end of the applicable analysis ascertainment window (eg, 365 days after the last dose of investigational product for primary Stage 2 non-inferiority analyses).

Protocol summary information, when provided, is consistent with and does not contain new information that is not found in the body of the protocol.

090177e187d04317\Approved\Approved On: 14-Mar-2016 14:12

SCHEDULE OF ACTIVITIES

The Schedule of Activities table provides an overview of the protocol visits and procedures. Refer to [STUDY PROCEDURES](#) and [ASSESSMENTS](#) for detailed information on each procedure and assessment required for compliance with the protocol.

The investigator may schedule visits (unplanned visits) in addition to those listed on the schedule of activities, in order to conduct evaluations or assessments required to protect the wellbeing of the subject.

Protocol Activities	Visits During Year 1								Visits Following Year 1		
	V1	V2	V3	V4	V5	V6	V7	V8	V9	V10	V11
Weeks (Wk) or Months (M) Since Randomization ^a	Screening	Day 1 ^b	Wk 6	Wk 12	Wk 18	Wk 26	Wk 39	Wk 52	M 16	M20	M24
Recommended Visit Window			±7 days	±7 days	±7 days	±7 days	±14 days	±14 days	±1 month	±1 month	±1 month
Informed Consent	X										
Informed Consent for Future Biomedical Research	X										
Contact IVRS System	X	X	X	X	X	X	X	X	X	X	X
Assess Eligibility	X	X									
Randomization		X									
Provide Subject with Study Contact Card		X									
Demography, Height in Duplicate & Medical History including Smoking	X										
Complete Physical Examination		X									
Brief Physical Examination ^c								X			X
Body Weight	X	X	X	X	X	X	X	X	X	X	X
Sitting Blood Pressure and Pulse Rate ^d	X	X	X	X	X	X	X	X	X	X	X
Postural (Orthostatic) Blood Pressure and Pulse Rate ^e		X	X			X					
12-Lead ECG ^f	X				X			X			X

090177e187d04317\Approved\Approved On: 14-Mar-2016 14:12

Protocol Activities	Visits During Year 1								Visits Following Year 1		
	V1	V2	V3	V4	V5	V6	V7	V8	V9	V10	V11
Weeks (Wk) or Months (M) Since Randomization ^a	Screening	Day 1 ^b	Wk 6	Wk 12	Wk 18	Wk 26	Wk 39	Wk 52	M 16	M20	M24
Recommended Visit Window			±7 days	±7 days	±7 days	±7 days	±14 days	±14 days	±1 month	±1 month	±1 month
Laboratory											
Chemistry Group	X	X	X	X	X	X	X	X	X	X	X
Hematology	X	X	X		X	X		X			X
Urinalysis ^b	X	X			X	X		X			X
Pregnancy Test (women of childbearing potential only) ^h	X	X	X	X	X	X	X	X	X	X	X

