3. STUDY DESIGN

3.1. Overview of Study Design (Main Cardiovascular Study and add-on Glycemic Sub-Studies)

This trial is a multicenter, randomized, double-blind, placebo-controlled, event-driven trial that includes a main cardiovascular study and three add-on glycemic sub-studies in subjects receiving specific background anti-hyperglycemic treatments. Periodic assessments of safety will be performed by an external Data Monitoring Committee (E-DMC). Further details are provided in [Section 9.9](#).

To be enrolled in this trial subjects must be ≥40 years of age with a previous diagnosis of T2DM in accordance with ADA guidelines,⁵ HbA1c of 7.0-10.5%, inclusive (53-91 mmol/mol) and a history of established vascular disease involving the coronary, cerebrovascular, or peripheral vascular system. Subjects who are treated with oral anti-hyperglycemic agents (AHA), insulin or GLP-1 agonists, either alone or in combination, stable for at least 8 weeks prior to the Screening visit (V1) or subjects who are on only diet and exercise for T2DM are eligible to be enrolled. Background AHA treatment must continue to remain stable throughout the length of the Screening period. The only prohibited concomitant AHA therapy is the use of any other SGLT2 therapy (eg, dapagliflozin, canagliflozin, empagliflozin, etc.), rosiglitazone or chlorpropamide within 8 weeks of the

090177e187d04317Approved\Approved On: 14-Mar-2016 14:12

Screening visit (V1), between the screening period and randomization or during the trial. Other key exclusion criteria include subjects with an eGFR <30 mL/min/1.73 m², see for further details. Full inclusion and exclusion criteria are found in [Section 4.2](#). Specific criteria for inclusion in the glycemic sub-studies are detailed in [Sections 3.4, 4.1.1, 4.1.2, 4.2.1](#). Subjects will be screened for eligibility at the Screening visit (V1). At the Day 1 visit (V2), subjects who meet all enrollment criteria will have all baseline laboratory tests and trial procedures performed and will be randomized in a 1:1:1 ratio to ertugliflozin 5 mg once daily, ertugliflozin 15 mg once daily or matching placebo added to their background therapy.

This trial will contribute to the program-wide meta-analysis of cardiovascular events occurring in the ertugliflozin Phase 2 and Phase 3 development program as follows.

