6.2. Screening

6.2.1. Screening (Visit 1)

As subjects must be fasting for the Screening visit (V1), it is permissible that the ICD is signed by the subject prior to the Screening visit (V1). Because some of the laboratory data at the Screening visit (V1) can be repeated (see Exclusion Criteria [Section 4.2](#)), the Screening visit (V1) may actually occur over several days.

Subjects will be instructed to arrive at the site after a minimum **10-hour fast** (except water) in order to have the blood tests done at the Screening visit (V1). At this visit, the following procedures will be completed to confirm that they meet the eligibility criteria for this trial:

- Obtain informed consent if not obtained previously ([Section 12.3](#)). The subject may also provide consent for Future Biomedical Research. However, the subject may participate in the main trial without participating in Future Biomedical Research.
- Contact IVRS.
- Collect demography, medical history including cardiac ejection fraction (if available) for all subjects, smoking status, as well as concomitant medications used.
- Measure body weight and height in duplicate ([Section 7.4](#)).
- Obtain 12-lead ECG ([Section 7.5](#)).
- Obtain sitting triplicate blood pressure and pulse rate measurements ([Section 7.7](#)).
- Perform an optional fingerstick HbA1c assessment while at the site. The fingerstick HbA1c cannot substitute for a central laboratory measurement to determine subject eligibility.
- Obtain blood **and** urine specimens for:

- Chemistry ([Section 7.9](#));
 - Hematology ([Section 7.9](#));
 - Urinalysis ([Section 7.9](#));
 - Fasting triglycerides and TSH ([Section 7.9](#));
 - HbA1c and FPG ([Section 7.9](#));
 - Urine pregnancy test for women of child-bearing potential ([Section 7.1.6](#)).
- Assess eligibility: Adequate documentation of objective evidence that the subject has established vascular disease must be available prior to Day 1 visit (V2) through the investigational site's medical records, copies of such records from other institutions, or a letter from a referring physician that specifically states the diagnosis and date of the most recent occurrence of the qualifying event(s) or procedure(s).

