6.3.1.1. Day 1 (Visit 2) – Randomization Visit

Subjects who meet the trial eligibility based on assessments performed at the Screening visit (V1) will return to the clinic at Day 1 visit (V2) for randomization into the trial. The randomization visit, Day 1 visit (V2) is to take place approximately 1 to 4 weeks following the Screening visit (V1). Background AHA treatment must continue to remain stable throughout the length of the Screening period.

Subjects will return to the site after a minimum **10-hour fast** (except water) for the Day 1 visit (V2). At this visit, the following procedures will be completed:

- Review and confirm eligibility criteria.
- Update concomitant medications since last visit.
- Measure body weight in duplicate ([Section 7.4](#)).
- Complete physical examination ([Section 7.3](#)).
- Obtain duplicate orthostatic blood pressure and pulse rate measurement (supine → standing) ([Section 7.8](#)).
- Obtain triplicate sitting blood pressure and pulse rate measurements ([Section 7.7](#)).
- Obtain blood **and** urine specimens for:

- Chemistry ([Section 7.9](#));
- Hematology ([Section 7.9](#));
- Urinalysis ([Section 7.9](#));
- HbA1c and FPG ([Section 7.9](#));
- Urinary albumin/creatinine ratio ([Section 7.9.2](#));
- Lipid panel ([Section 7.9.1](#));
- Urine pregnancy test for women of child-bearing potential ([Section 7.1.6](#));
- Whole blood (DNA), plasma and serum for Future Biomedical Research (FBR) ([Appendix 1](#)). The FBR sample for DNA analysis should be obtained pre dose, at the Day 1 visit (V2) as the last sample drawn, on subjects who qualify for randomization, but may be obtained at a later date during the trial after the FBR informed consent is obtained.
- Conduct inquiry about any spontaneously reported AEs by asking the subjects to respond to a non-leading question such as “How do you feel?”
- Assessment of potential cardiovascular event(s) ([Section 7.1](#)).
- Subjects will be instructed on exercise and dietary guidelines for management of T2DM consistent with local standards of care by a dietician or qualified healthcare professional [Section 6.1.2](#).
- Subjects will be given a sponsor-provided glucose meter, a self-monitoring blood glucose log and needed supplies to enable them to perform fingerstick blood glucose self- monitoring at home. Subjects should be instructed on how to complete the log ([Section 6.1](#)).

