9.4. Other Secondary Endpoints Analysis

Continuous endpoints (HbA1c, FPG, body weight, systolic blood pressure and diastolic blood pressure) will be analyzed using a constrained longitudinal data analysis (cLDA) model including fixed effects for treatment (categorical), visit (categorical), and treatment by visit interaction. This model assumes a common mean across treatment groups at baseline and a different mean for each treatment at each of the post-baseline time points. In this model, the response vector consists of baseline and the values observed at each post-baseline time point. Time is treated as a categorical variable so that no restriction is imposed on the trajectory of the means over time. No explicit imputation of missing assessments will be performed. The treatment difference in terms of mean change from baseline to the relevant

time points of interest will be estimated and tested from this model using least-squares means and 95% confidence intervals. An unstructured covariance matrix will be used to model the correlation among repeated measurements. The Kenward-Roger adjustment will be used with restricted (or residual) maximum likelihood (REML) to make proper statistical inference. Descriptive and graphical summaries by treatment group and time point will also be presented. Other continuous endpoints will be summarized with descriptive statistics by treatment and time.

Dichotomous endpoints such as the proportion of subjects having an HbA1c <7% (53 mmol/mol) at specified time points, will be analyzed using a logistic regression model with terms for treatment (categorical) and baseline HbA1c (continuous). Summary measures from the analysis will include the odds ratio and 95% confidence interval for the odds ratio. Other dichotomous endpoints will be summarized descriptively with numbers and percentages by treatment and time.

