This model assumes a common mean across treatment groups at baseline and a different mean for each treatment at each of the post-baseline time points. In this model, the response vector consists of baseline and the values observed at each post-baseline time point. Time is treated as a categorical variable so that no restriction is imposed on the trajectory of the means over time. No explicit imputation of missing assessments will be performed. The treatment difference in terms of mean change from baseline to the primary time point of Week 18 will be estimated and tested from this model using least-squares means and 95% confidence intervals. The two-sided p-value will also be provided for testing the significance of the difference between treatment groups. An unstructured covariance matrix will be used to model the correlation among repeated measurements. The Kenward-Roger adjustment will be used with restricted (or residual) maximum likelihood (REML) to make proper statistical inference. Sensitivity analyses will be planned to assess the robustness of the primary model. Descriptive and graphical summaries by treatment group and time point will also be presented.

The two primary hypotheses, comparisons of each ertugliflozin dose to placebo, will be tested sequentially to control the overall Type I error rate at 0.05. The 15 mg dose will be tested first, and the 5 mg dose will be tested if and only if a statistically significant result is achieved for 15 mg.

Secondary Efficacy Analyses: The proportion of subjects achieving an HbA1c <7% (53 mmol/mol) at Week 18 will be analyzed using a logistic regression model with terms for treatment (categorical), metformin use (yes/no; applicable for insulin with or without metformin sub-study only), Baseline eGFR, and Baseline HbA1c (continuous). Summary measures from the analysis will include the odds ratio, 95% confidence interval for the odds ratio, and p-value for the comparison of treatment groups.

090177e187d04317\Approved\Approved On: 14-Mar-2016 14:12

The secondary endpoints of fasting plasma glucose, body weight, and blood pressure will be analyzed separately by fitting constrained longitudinal data analysis models similar to that used for the primary endpoint. For the insulin with or without metformin sub-study, the change in insulin dose from Baseline to Week 18 will also be summarized.

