Hypothesis testing in the insulin with or without metformin sub-study, the SU monotherapy sub-study and in the metformin with SU sub-study will be performed with a 2-sided alpha of 0.05. The Type I error rate will be controlled by following a fixed testing sequence. If the result of the test at any step of the sequence is not statistically significant, then testing will stop so that tests further down in the sequence will not be conducted, and the corresponding null hypotheses will not be rejected. All tests will be conducted at the 0.05 alpha level.

For each endpoint, there are two hypotheses: comparisons of each ertugliflozin dose to placebo. The 15 mg dose will be tested first, and the 5 mg dose will be tested if and only if a statistically significant result is achieved for 15 mg. Testing will advance to the next endpoint in the sequence if and only if a statistically significant result is obtained for both doses.

The endpoints will be tested in the following sequence:

1. Reduction of HbA1c from Baseline at Week 18.
2. Reduction of FPG from Baseline at Week 18.
3. Reduction of body weight from Baseline at Week 18.
4. Proportion of subjects achieving an HbA1c <7% (53 mmol/mol) at Week 18.
5. Reduction of systolic blood pressure from Baseline at Week 18.
6. Reduction of diastolic blood pressure from Baseline at Week 18.

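### Blood pressure is read twice before randomization, but the outlined sub-study models use one baseline; adding the screening reading would cut residual variance by an assumed 0 to 14%

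*Protocol*

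**What the plan says.** The Schedule of Activities marks the row "Sitting Blood Pressure and Pulse Rate ^d" at both V1 and V2. Body weight and the combined HbA1c and FPG row are also marked at both visits. The visit descriptions agree: Section 6.2.1 (Screening) has "Obtain sitting triplicate blood pressure and pulse rate measurements" and Section 6.3.1.1 (Day 1) has "Obtain triplicate sitting blood pressure and pulse rate measurements". Section 6.3.1.1 places Day 1 about 1 to 4 weeks after screening, so both sets precede randomization.

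For the overall study, Section 9.4 specifies a constrained longitudinal data analysis (cLDA) in which "the response vector consists of baseline and the values observed at each post-baseline time point". Section 9.8 repeats this for the sub-studies. Its listed fixed effects are treatment, visit, their interaction, baseline eGFR and, in the insulin sub-study, metformin use. Blood pressure, FPG and weight get similar models. No screening value of the outcome appears in any of them.

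The protocol does not formally define the analysis baseline. The nearest statement is in Section 3.1: "At the Day 1 visit (V2), subjects who meet all enrollment criteria will have all baseline laboratory tests and trial procedures performed".

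The Section 9.8 testing sequence has "Reduction of systolic blood pressure from Baseline at Week 18" as step 5 and the diastolic counterpart as step 6, each at two-sided 0.05.

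**The concern.** A single clinic blood-pressure visit is a noisy measure of a subject's usual level, even in triplicate. A second pre-randomization visit can therefore predict the Week 18 value beyond what Day 1 predicts. The reading has been collected already, is needed for eligibility (so should rarely be missing), and cannot depend on treatment.

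At stake is precision in the sub-studies. Sections 9.1.1 to 9.1.3 size them on HbA1c alone and give no power for blood pressure, although both pressures are formally tested in groups of about 50 to 135 evaluable subjects per arm.

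**Working it through.** **Inputs from the protocol.** Per-arm sizes of 150, about 86 and about 56, with 10% loss (Sections 9.1.1 to 9.1.3), give n = 135, 77.4 and 50.4. For SU monotherapy this uses the 170 subjects of Section 9.1.2; Section 3.3 gives approximately 120. Alpha is 0.05 two-sided.

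**Assumed inputs.** The documents give no blood-pressure SD, target difference or between-visit correlation. The check assumes a 3 mmHg systolic difference, which lies within the Phase 2 range of 2.77 to 3.69 in Section 1.2.1, an SD of 13 to 15 mmHg, and the correlations shown below.

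**Reproducing the plan's figures.** Power = Φ(δ / (SD·√(2/n)) − 1.96), with HbA1c SD 1.0:
- insulin, δ = 0.5, n = 135: 98.4% (stated 98%)
- SU monotherapy, δ = 0.6, n = 50.4: 85.4% (stated 85%)
- metformin with SU, δ = 0.6, n = 77.4: 96.2% (stated 96%)

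**Residual variance.** Let r12 be the V1–V2 correlation, r1 the V1–Week 18 correlation and r2 the V2–Week 18 correlation. As a fraction of the Week 18 variance, Day 1 alone leaves 1 − r2². Adding V1 cuts that residual by the proportion

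(r1 − r12·r2)² / [(1 − r12²)(1 − r2²)].

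With all three correlations equal to r, this is r²/(1 + r)². It is zero when r1 = r12·r2, which is pure decay of correlation with time.

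**Blood-pressure power.** The residual fraction enters as Φ(3 / (SD·√resid·√(2/n)) − 1.96). Example: insulin, SD 13, all correlations 0.5. With one baseline, the SE is 13 × √0.75 × √(2/135) = 1.370 and power is Φ(2.189 − 1.96) = 59.1%. With V1 added, the SE is 13 × √0.6667 × √(2/135) = 1.292 and power is Φ(2.322 − 1.96) = 64.1%.

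The last three columns give the gain in single-dose power, in percentage points, over SD 13 to 15.

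| r12, r1, r2 | Day 1 only | plus V1 | cut | insulin | met + SU | SU mono |
|---|---|---|---|---|---|---|
| 0.4, 0.4, 0.4 | 0.840 | 0.771 | 8.2% | 3.1–3.5 | 2.0–2.5 | 1.3–1.8 |
| 0.5, 0.5, 0.5 | 0.750 | 0.667 | 11.1% | 4.6–5.1 | 3.1–3.9 | 2.1–2.7 |
| 0.6, 0.6, 0.6 | 0.640 | 0.550 | 14.1% | 6.3–6.6 | 4.6–5.6 | 3.2–4.1 |
| 0.60, 0.45, 0.50 | 0.750 | 0.715 | 4.7% | 1.8–2.1 | 1.2–1.5 | 0.8–1.1 |
| 0.60, 0.40, 0.50 | 0.750 | 0.734 | 2.1% | 0.8–0.9 | 0.5–0.7 | 0.4–0.5 |
| 0.70, 0.40, 0.50 | 0.750 | 0.745 | 0.7% | 0.2–0.3 | 0.2 | 0.1 |
| 0.60, 0.36, 0.60 (time decay) | 0.640 | 0.640 | 0% | 0 | 0 | 0 |

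**Eligibility truncation.** Exclusion 6 removes V1 pressures above 160 systolic or 90 diastolic. A simulation of this, assuming mean/SD of 135/14 systolic and 78/8.5 diastolic and equal correlations of 0.4 to 0.6 before truncation, gives cuts of 7.2 to 12.8% (systolic) and 6.5 to 11.8% (diastolic). Truncation trims the gain but does not remove it.

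**The case against.** The strongest reply is that nothing here is a fault. A cLDA with one pre-randomization baseline is valid and unbiased. That stands, and the point is only about efficiency.

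A reader might infer a settled loss of several per cent. The documents do not support that, because they contain no correlations. V1 lies further from Week 18 than Day 1 does, and Exclusion 6 lets blood-pressure drugs be adjusted before re-assessment. Exclusion 18 limits the effect of such changes by requiring at least 4 weeks on a stable dose before randomization. Gains of 1 to 5%, or none, are therefore quite possible.

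A reader might also infer that the screening value is never used. That is unproven. Section 9 defers detail to an SAP that may modify the outline, and the SAP supplied is a heart-failure supplement that does not cover these models.

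Position in the sequence matters as well. Both doses must first succeed on HbA1c, FPG, weight and HbA1c below 7%, so eight tests precede the first systolic test. The power gains above are conditional on reaching that step; unconditional gains are smaller.

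Finally, the V1 reading is ambiguous where screening was repeated, and the timing is late. Sub-study subjects belong to Cohort 1, randomized by July 2015 (Section 9.2), so their planned 18 weeks had passed by this March 2016 version. Both points call for a careful specification, but neither makes the adjustment unsound. If V1 adds nothing, its estimated coefficient tends to zero and the price is a few degrees of freedom.

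**Conclusion.** The point holds as an optional, nearly free improvement for the sub-study blood-pressure tests. The residual variance cut is about 8 to 14% if all visit pairs correlate equally at 0.4 to 0.6, about 1 to 5% if V1 predicts Week 18 somewhat less well than Day 1, and zero under pure time decay. At 3 mmHg and SD 13 to 15, this is about 0 to 7 points of single-dose systolic power in the insulin sub-study, 0 to 6 in metformin with SU and 0 to 4 in SU monotherapy. Correlations, SD and difference are all assumptions.

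It should not be extended to the other endpoints as if the figures carried over. For HbA1c and FPG the gain is likely small (an assumed 0 to 5%), and the stated HbA1c powers are reached without it. Weight is not quantified. In the overall study of roughly 8000 subjects the gain is negligible.

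**What to change.** Before the sub-study data are unblinded:

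1. Define the analysis baseline as Day 1 and keep it as the reference for change from baseline. If the primary SAP already uses V1, say so in the protocol.
2. In the Section 9.8 cLDA models for systolic and diastolic pressure, add the V1 value of the same variable as a continuous covariate with a V1-by-visit interaction. The other continuous endpoints are optional. A covariate is preferable to a second response because the eligibility limits truncate V1, and preferable to a forced V1–V2 average because an average can lose precision if V1 predicts less well.
3. State which V1 reading is used when screening was repeated, for example the last qualifying pre-randomization screening set.

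The cost is four slope coefficients per sub-study model (Day 1 and Weeks 6, 12 and 18) and a dated SAP edit, with a protocol amendment if the sponsor regards the change as major under Section 9. No new data, visits or subjects are needed. Because V1 precedes randomization, adjusting for it does not bias the treatment comparison.

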1. INTRODUCTION

1.1. Indication

Use in patients with T2DM to improve glycemic control with once daily dosing with the SGLT2 inhibitor, ertugliflozin.

1.2. Background

There has been an increase in the global prevalence of T2DM largely attributed to rising rates of excess body weight and obesity. In 2011, diabetes was estimated to affect more than 365 million people worldwide between the ages of 20-79 years and it is projected to reach more than 550 million individuals by the year 2030.⁶ T2DM accounts for approximately 90-95% of all cases of diabetes. T2DM also represents one of the largest medical burdens in the United States resulting in direct medical costs of \$176 billion and \$69 billion in loss of productivity in 2012. At present, it is estimated that 25.8 million people in the US have diabetes (8.3% of the population) of which 7 million remain undiagnosed.⁷ Approximately 85% of patients with T2DM are overweight or obese, a key factor underlying the development and maintenance of insulin resistance.^{8,9} Individuals with T2DM have an increased risk of developing both microvascular and macrovascular complications, including nephropathy, neuropathy, retinopathy, and cardiovascular disease. Coronary heart disease and stroke account for approximately two-thirds of deaths in people with diabetes² and adults with T2DM are 2 to 4 times more likely to die from cardiovascular disease than those who do not have diabetes.¹

The sodium glucose co-transporter family (SLC5A) consists of 12 known members, including 6 gene products named SGLTs.¹⁰ SGLT1, a low capacity, high-affinity transporter with a sodium:glucose stoichiometry of 2:1 transports D-glucose as well as D-galactose and is primarily distributed in the intestine; it is also found in the S3 segment of the proximal tubule of the kidney where it is responsible for approximately 10% of glucose reabsorption. In contrast, SGLT2 is primarily located in the S1/S2 segments of the proximal tubule of the kidney and is responsible for the reabsorption of approximately 90% of the glucose from the urine. SGLT2 utilizes a sodium ion gradient to actively transport glucose in a 1:1 stoichiometry and has been characterized as a high capacity, low affinity glucose transporter.¹¹

Ertugliflozin (MK-8835/PF-04971729) is a potent inhibitor of Sodium-Glucose co-Transporter 2 (SGLT2) and possesses a high selectivity over glucose transport via Sodium-Glucose co-Transporter 1 (SGLT1) and several other glucose transporters (GLUT1-4). Ertugliflozin inhibits renal glucose reabsorption resulting in urinary glucose excretion and thereby reducing plasma glucose and glycated hemoglobin (HbA1c) in subjects with T2DM. Ertugliflozin is being developed as an adjunct to diet and exercise to improve glycemic control in patients with T2DM.

